## I. PURPOSE OF THE STUDY AND BACKGROUND

### A. Purpose of the Study

The proposed study “Integrated Community-Clinical Linkage Model to Manage Diabetes among South Asians” aims to test the effectiveness of a multi-level diabetes management intervention compared to usual care. The primary outcome is reduction in hemoglobin A1c (HbA1c) for patients with baseline HbA1c of  $>7\%$ . The secondary outcomes include enhanced use of community and social services and increased self-efficacy.

The integrated intervention involves:

1. An electronic health record (EHR) intervention for primary care providers (PCPs) utilizing embedded alerts to identify South Asian patients with uncontrolled diabetes.
2. Registry-driven community health worker (CHW)-led health coaching for patients. Using a stepped-wedge design, we will implement the study in 20 NYC PCP clinics enrolling 886 South Asian patients at- risk for Type 2 Diabetes Mellitus (T2DM).
3. Linkage to culturally relevant community-level resources
4. CHW-integration into primary care teams. The project will leverage Health Information Technology (HIT) tools to support integration of CHWs in healthcare teams, feedback between healthcare providers and CHWs, and establish a referral mechanism between CHWs, patients, and community resources

In addition, using a mixed-methods approach and the RE-AIM evaluation framework, we aim to systematically assess the implementation process and delineate factors that influence adoption, sustainability, and scalability of the integrated EHR-CHW intervention within applied practice settings.

This will be achieved through the completion of:

5. Provider Surveys (n=80) to capture data on satisfaction with workflow before and after intervention, information sources for EHR-CHW initiatives before and after intervention, acceptability of and satisfaction with the integrated EHR-CHW intervention, and barriers and facilitators of point-of-care use of the tools.

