There are four primary research groups for this study: 1) 446 treatment participants who will receive the CHW intervention; 2) 446 waitlisted control participants who may receive the CHW intervention as a point of service at a later point (de-identified EHR data collection only); 3) 40 subjects who will participate in provider surveys; and 4) 35 subjects who will participate in qualitative key informant interviews.

Figure 1. Recruitment, Enrollment, and CHW Intervention Timeline

Participant A�elar Projections	Year 1		Year 2		Year 3		Year 4		Year 5		Enrollment by wave 2022	Cumulative enrollment for entire study				
	Apr - June 2018	July - Sept 2018	Oct - Dec 2018	Jan - Mar 2019	Apr - June 2019	July - Sept 2019	Oct - Dec 2019	Jan - Mar 2020	Apr - June 2020	July - Sept 2020	Oct - Dec 2020	Jan - Mar 2021	Apr - June 2021	July - Sept 2021	Oct - Dec 2021	Jan - Mar 2022
Wave 1																
PCP1			Recruit/ Enroll N=44	CHW intervention		CHW intervention										
PCP2			Recruit/ Enroll N=44	CHW intervention		CHW intervention										
PCP3			Recruit/ Enroll N=44	CHW intervention		CHW intervention										
PCP4			Recruit/ Enroll N=44	CHW intervention		CHW intervention										
PCP5			Recruit/ Enroll N=44	CHW intervention		CHW intervention										
PCP6			Recruit/ Enroll N=44	CHW intervention		CHW intervention										
PCP7			Recruit/ Enroll N=44	CHW intervention		CHW intervention										
Wave 2																
PCP8					Recruit/ Enroll N=44	CHW intervention		CHW intervention								
PCP9					Recruit/ Enroll N=44	CHW intervention		CHW intervention								
PCP10					Recruit/ Enroll N=44	CHW intervention		CHW intervention								
PCP11					Recruit/ Enroll N=44	CHW intervention		CHW intervention								
PCP12					Recruit/ Enroll N=44	CHW intervention		CHW intervention								
PCP13					Recruit/ Enroll N=44	CHW intervention		CHW intervention								
Wave 3																
PCP14					Recruit/ Enroll N=44	CHW intervention		CHW intervention								
PCP15					Recruit/ Enroll N=44	CHW intervention		CHW intervention								
PCP16					Recruit/ Enroll N=44	CHW intervention		CHW intervention								
PCP17					Recruit/ Enroll N=44	CHW intervention		CHW intervention								
PCP18					Recruit/ Enroll N=44	CHW intervention		CHW intervention								
PCP19					Recruit/ Enroll N=44	CHW intervention		CHW intervention								
PCP20					Recruit/ Enroll N=44	CHW intervention		CHW intervention								

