## *2. Data collection and consenting with waitlisted control participants*

The NYU study team will only be collecting de-identified EHR data with control participants (n=443). EHR data will include clinical measures related to diabetes (e.g., HbA1c, BMI) and will be obtained from regularly generated diabetes registry lists that practices generate as part of quality improvement initiatives and these measures will be tracked over time. The PCPs will be conducting the de-identification and the link to the unique identifier will remain with the PCP staff. NYU study team members will not have access to these links. Beyond EHR data collection, no other data collection will occur with control participants (e.g., no survey data collection) and the control group will not have any interaction with study personnel for the purposes of research. PCPs will invite control participants to CHW education sessions at a later time (post round 1 of CHW intervention with treatment participants) as a point of service (i.e., not for research

purposes). The PCPs themselves are not involved in the research aside from providing NYU with de-identified EHR data.

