## A2. Data Collection

### *EHR Data*

Data will be extracted from the PCP clinics' EHR systems every 6 months. De-identified EHR data will be collected from both treatment and control participants.

The process for collecting de-identified patient data is described here: This will entail PCP staff exporting de-identified patient information via a secure sftp site to a central repository managed by NYU. In order to de-identify patient information, PCP staff will generate a set of unique study identifiers to assign to treatment and control patients by associating a specific study number with a specific medical record number in the EHR system. The table of study identifiers and corresponding medical record numbers for the duration of the study in a secure and locked location in their respective clinics. All other potentially identifying data will also be stripped from the dataset prior to extraction. Only the PCPs will retain the table necessary to link patient identifiers and the study ID. Using this method, we will ensure that patient confidentiality is maintained, but that patients who are observed more than once will have the same study ID in each extraction, which is necessary for the planned analyses. Using the described approach, a pre-defined set of patient data will be exported every 6 months from the clinics' EHR systems into a de-identified Excel spreadsheet or delimited text file. Data elements will be based on functionalities of EHR platforms and will include patient demographic information such as year of birth, gender, race/ethnicity, diagnoses, medications, and laboratory results.

Follow-up height, weight and HbA1c measures will be obtained during routine office visit at six months. Scheduled office visits will be tracked via quarterly data pulls from the PCPs. If no visit is scheduled during the follow-up period, project CHWs will conduct follow-up calls to schedule patients for a height and weight recording at the clinic. Patient travel incentives will be provided to facilitate follow-up data collection.

De-identified EHR data will include the following:

- Clinic ID, patient study ID, and demographics - gender, age, race/ethnicity (if available), Language (if available)
  - Any diagnoses for: hypertension, diabetes, pre-diabetes, and high cholesterol during the study period , including month and year of diagnosis
  - Height and weight data during the data collection period, Month and year of measurement

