## B. Data Analysis and Data Monitoring

### B1. Aim 1 Analysis

AIM 1: Specific Aim I: Test the effectiveness of a multi-level diabetes management intervention compared to usual care. The primary outcome is reduction in HbA1c for patients with baseline HbA1c of >7%. The secondary outcomes include enhanced use of community and social services and increased self-efficacy.

*Hypothesis:* Individuals receiving the multi-level diabetes management intervention will be more likely to achieve >0.5% reduction in HbA1c 6 months following the index office visit than individuals receiving care as usual.

The analysis of the effect of intervention on the outcome measure will proceed using a Generalized Linear Mixed Model (GLMM). In particular, we will use a random effects model that assumes a binomial distribution with a logit link function. The comparison will make no linear assumption about the time trend for each outcome over the course of the trial. The model will be as follows:

$$(1) \quad \text{logit}(Y_{ijt}) = \mu + \alpha_j + \theta_t + \tau C_i,$$

where  $Y_{ijt} = 1$  if the  $i^{\text{th}}$  subject attached to the  $j^{\text{th}}$  clinic at time quarter  $t$  achieves an HbA1c reduction of 0.5% or more within six months following the index visit,  $Y_{ijt} = 0$  otherwise.  $\alpha_j$  is a random effect for clinic  $j$  with mean 0 and variance  $\sigma^2_b$ .  $\theta_t$  is a time-specific effect of quarter  $t, t \in (1, 2, \dots, 12)$ .  $C_i$  is an indicator variable, and  $C_i = 1$  if individual  $i$  receives care under the EHR/CHW intervention,  $C_i = 0$  if individual  $i$ .  $\tau$  represents the treatment effect of the intervention. The model will be fit using the LME4 package using R software. The hypothesis will be tested using two-sided level of significance  $\alpha = .05$ . Because outcome data will be derived from administrative data, we do not anticipate missing data. However, in the event that there is missing data, we will use multiple imputation under the assumption of data missing at random (MAR). This is consistent with following an intent-to-treat protocol. Sex as a biological variable will be addressed by exploring gender as a potential moderator of intervention effects.

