#### *Control Participants*

The NYU study team will only be collecting de-identified EHR data with control participants. The PCPs will be conducting the de-identification and the link to the unique identifier will remain with the PCP staff. NYU study team members will not have access to these links. Beyond EHR data collection, no other data collection will occur with control participants (e.g., no survey data collection) and the control group will not have any interaction with study personnel for the purposes of research. PCPs will invite control participants to CHW education sessions as a point of service (i.e., not for research purposes). For these reasons, we will not be obtaining consent with control participants.

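### Aim 1 lists self-efficacy and service use as secondary outcomes of a test against usual care, but controls supply no self-efficacy data, and no service-use measure is named or listed in their extract

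*Combined protocol and SAP*

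**What the plan says.** Section I.A says the study "aims to test the effectiveness of a multi-level diabetes management intervention compared to usual care". Section B1 (Aim 1 Analysis) repeats this as "Test the effectiveness of a multi-level diabetes management intervention compared to usual care" and then adds: "The secondary outcomes include enhanced use of community and social services and increased self-efficacy".

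The data come from these sources:

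- **Treatment participants.** Section C2, item 1, provides a baseline survey within two weeks of consent and a follow-up survey at about six months. Self-efficacy items are to be taken from three published scales: one of personal mastery, one of self-esteem and one of self-efficacy. Sections C2 and VI.G both give evaluation of the CHW intervention's effectiveness as the purpose of the follow-up survey.
- **Controls.** Section C2, item 2, says: "Beyond EHR data collection, no other data collection will occur with control participants (e.g., no survey data collection". Section VI.G repeats this and concludes that "we will not be obtaining consent with control participants". The list of research groups in section C1 likewise limits controls to de-identified EHR data.
- **EHR extract.** Section III.A2 describes its content as "patient demographic information such as year of birth, gender, race/ethnicity, diagnoses, medications, and laboratory results". The itemised list that follows adds height, weight, HbA1c and lipids.

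The hypothesis and model in B1 and the power calculation after it concern HbA1c only. No analysis is given for either secondary outcome.

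**The concern.** A secondary outcome placed under a comparative aim will be read as something compared between arms. For self-efficacy the design cannot supply the second arm. A before-after change in treated patients mixes any intervention effect with secular change, regression to the mean and pandemic-period change. Section C2 records that sessions moved to remote delivery because of COVID-19. The staggered waves and rounds in section C1 might give some calendar overlap, but no analysis that uses it is planned. Because the follow-up survey is described as evaluating effectiveness, a one-arm change could be reported as an effect against usual care.

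Service use raises a different problem. With no measure or source named in the plan text, both could be chosen after the data have been seen.

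**Working it through.** **1. The plan's own figure.** The only stated figure is for HbA1c: more than 80% power with 886 participants, a 10-point difference, two-sided 0.05 and 15% loss. The control rate is not given. Assuming 35% against 45%, with pooled variance:

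n per arm = [1.960·sqrt(2·0.40·0.60) + 0.842·sqrt(0.35·0.65 + 0.45·0.55)]² / 0.10² = (1.358 + 0.580)² / 0.01 ≈ 376.

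376 / 0.85 = 442.4, rounded up to 443 per arm and 886 in total. With 376 evaluable per arm, power is 0.801 at this control rate. It ranges from 0.784 to 0.996 over assumed control rates of 5% to 50%. The figure is reproduced under the 35% assumption. There is no corresponding figure for either secondary outcome.

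**2. Self-efficacy.** Section II gives 443 treatment and 443 control participants. The only source is the patient survey (C2, item 1). Controls surveyed: 0 (C2, item 2; VI.G).

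- Controls who can have a value: 0/443 = 0% (0/446 by the research-group list in C1).
- Participants who can have a value: at most 443/886 = 50%, all in one arm.

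B1 allows multiple imputation under missing at random. That cannot supply the comparison, because the outcome is observed in no control.

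**3. How a one-arm change would look.** Assume the plan's 15% loss applies to the survey: 443 × 0.85 = 376.55, taken as 376. For one score, ignoring clustering, the 95% CI half-width is 1.96/sqrt(376) = 1.96/19.39 = 0.10 SD of the change score. The documents give no SD, so this stays in SD units. An average shift of little more than 0.1 SD, from any cause, would exclude zero. The result could be precise and still say nothing about usual care.

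**4. Service use.** The places that come nearest to a measure are:

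| Source | Where | Status |
|---|---|---|
| CHW referrals | C2; III.A1 | intervention activity, not defined as an outcome |
| Progress notes, encounter reports | C2 | CHW records, not linked to an outcome |
| Survey topics on health access and faith-based support | C2 | the second sits under social support; neither is named as service use |
| Healthfirst claims | VI.G | in the treatment participants' consent only, not linked to an outcome |
| Survey forms | Appendix list | forms not part of the documents |

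Outcome measures for service use named in the plan text: 0. Service-use fields in the listed EHR extract: 0.

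**The case against.** Four points can be made for the plan.

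- **Same measures in both arms.** Section III.A2 says data collection is the same for treatment and control participants. That sentence closes the EHR section, and the next one restricts further data to consented treatment participants. C2 and VI.G exclude control surveys outright. This does not rescue self-efficacy.
- **The EHR list may be open.** III.A2 ties the data elements to what each EHR platform can do, and C3 and III.A1 describe making systems that link patients to community resources available through the EHR. A reader might infer that controls certainly have no service-use data, with the same firmness as for self-efficacy. The documents do not support that. They show only that no measure is named and no such field is listed. Nor do they show that the treatment arm lacks service-use data, since the survey forms cannot be seen. This part of the objection stands.
- **No promised conclusion.** A reader might infer that Aim 1 commits the trial to conclusions on both outcomes. It does not: hypothesis, test and power are set for HbA1c only. This stands too, and the fault is one of labelling. Still, the text does not limit these outcomes to description, as B2 does for the provider survey, and the effectiveness wording for the patient survey points the other way.
- **Deliberate choice.** Leaving controls uncontacted and without consent is a design decision. It is not disputed here.

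**Conclusion.** The plan is wrong as written on a limited point. It lists two secondary outcomes under a comparison with usual care that the described data cannot deliver.

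- **Self-efficacy: firm.** No control can have a value, so only an uncontrolled change in the treatment arm is available. The effectiveness wording in C2 and VI.G goes beyond that. This rests only on the exclusion of control surveys.
- **Service use: as listed.** No measure or source is named in the plan text and no such field appears in the control extract, so no between-arm comparison is possible as the plan stands. A suitable EHR field, if one exists and is extracted in both arms, would change this.

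A reader might infer that the main result is also compromised. It is not: HbA1c comes from the EHR in both arms.

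**What to change.** 1. In I.A and B1, state that self-efficacy is measured in treatment participants only. Report it as a descriptive baseline-to-6-month change with a 95% CI, on one score named before analysis from the scales in C2, with no comparison with usual care and no effectiveness claim.
2. Amend the effectiveness wording about the follow-up survey in C2 and VI.G to match.
3. Name the service-use measure and its source before analysis. Compare arms only if the source is an EHR field extracted for both arms within the terms of C2, item 2, and III.A2. Otherwise report it descriptively in the treatment arm, with no effectiveness claim.

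The cost is wording in four places, one named score and one named service-use measure. No control survey is requested, since that would need the contact and consent the plan excludes. The downside is a weaker claim for the two secondary outcomes.

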### C. Study Design

#### C1. Overall Design/Clinic Selection/Clinic Enrollment

We will use a randomized controlled trial design with staggered-entry and a waitlisted control group to compare the effectiveness of an alert and registry-driven CHW-led coaching compared with usual care among patients with HbA1c at  $>7\%$ . Randomization will be at the individual-level and stratified by PCP, meaning eligible treatment and control participants will be randomized for each PCP. PCPs will be clustered into waves, aligning with the original stepped-wedge design. Entry into the study will be staggered in three waves, with each wave consisting of six to seven PCPs (See Figure 1). All 20 PCPs will be recruited and enrolled by month 6 of Year 1 (study period 6, Figure 1), and we will assign 6-7 practices into each of the 3 waves upon enrollment. For each PCP, there will be a total of two rounds of consecutive six-month CHW intervention periods for the treatment group: 1 month for recruitment and enrollment of treatment participants and five months of community health worker-led group education sessions (approximately one session per month). Data related to the study outcomes will be extracted from EHR systems a total four times (baseline, 6 month, 12 month, and 18 month) for each PCP; we will be comparing EHR data from 443 treatment participants with 443 control participants. Prior to allocation into treatment group, each treatment participant will be matched to a control participant based on age, gender, and BMI. Treatment participants will be split into two groups and assigned to either first or second round. All control participants will be waitlisted during the first round and will be offered the full CHW group education sessions during the second round as a point of service (i.e., not for research purposes).

Randomization at each PCP will occur during the first round. PCPs will be placed into waves based on geographic location and CHW caseload considerations. PCPs will be eligible for participation if they have a) an overall patient volume of  $N \geq 1000$  ; b) at least 70% of the patient population is South Asian; and c) the practice has used EHR for at least 12 months. All PCPs will sign a Memorandum of Understanding (MOU) between the PCP and NYU outlining study commitments.

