### *CHW Intervention*

Inclusion Criteria: Participants will be eligible for study participation if they meet the following criteria: a) are of South Asian ethnicity; b) are at least 21 years of age and younger than age 75, c) had an appointment with a physician or mid-level clinician for routine non-emergent primary care in the last 12 months; d) a diagnosis of diabetes and e) an HbA1c reading of >7 in the last 12 months.

Exclusion Criteria: Patients under the age of 21 and older than 75 will be excluded. Pregnant women and all visits with an obstetrician gynecologist are excluded. Patients will be excluded if they were enrolled in a CHW led hypertension or diabetes education intervention in the past five years.

No children or vulnerable subjects will be enrolled in this study.

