  - All lab results for: HbA1c, lipid profile during the study period, Month and year of measurement

All data collection measures and procedures will be the same for treatment participants as control patients with the exception that data will no longer be de-identified. PHI and other data will be collected from treatment participants and with their full consent only. Treatment participants will also have the option to authorize staff to take photographs, video and audio for the purpose of disseminating health promotion and CHW led health intervention work in the audio/video consent form.

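### The primary HbA1c responder model leaves out baseline HbA1c and the matching factors, and no analysis of HbA1c as a continuous value is prespecified

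*Combined protocol and SAP*

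**What the plan says.** Section III.B1 (Aim 1 Analysis) states: "The primary outcome is reduction in HbA1c for patients with baseline HbA1c of >7"%. The hypothesis turns this into a responder comparison, in which intervention patients "will be more likely to achieve >0.5% reduction in HbA1c 6 months following the index office visit". The outcome Y in equation (1) equals 1 if the patient "achieves an HbA1c reduction of 0.5% or more within six months following the index visit". For the analysis, "we will use a random effects model that assumes a binomial distribution with a logit link function". The terms are an intercept, a random clinic effect, quarter effects and the treatment indicator. Gender is mentioned only as a possible moderator to be explored.

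Section I.C1 states that, before allocation, "each treatment participant will be matched to a control participant based on age, gender, and BMI". Section II admits patients with "an HbA1c reading of >7 in the last 12 months", with no upper limit. Section III.A2 lists age, gender, height and weight for both arms, and "All lab results for: HbA1c, lipid profile during the study period, Month and year of measurement".

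The power paragraph in III.B1 sizes the trial on a 10% difference in the proportion with a fall of at least 0.5%. Section I.B5 cites a 0.2% average HbA1c reduction from community health worker (CHW) programmes, with reductions above 0.5% in patients with the highest values, and calls 0.5% clinically significant.

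**The concern.** There are three gaps.

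- **No covariates.** Baseline HbA1c enters Y through the change score but is not a covariate. Patients with high entry values have more room to fall and will regress towards the mean, so baseline should predict response strongly. Leaving it out wastes precision. The arms are matched on age, gender and BMI, but the model does not use these factors either.
- **No continuous analysis.** Aim 1 names HbA1c reduction, yet nothing in the plan estimates the mean difference. An effect near the 0.2% average could go undetected by the responder test, and any later analysis of means would be post hoc.
- **Two cut-offs.** A patient whose HbA1c falls by exactly 0.5 is a responder under the model and the power section but not under the hypothesis.

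**Working it through.** **1. The plan's own figure.** Inputs from the power paragraph: 886 patients, 1:1, two-sided 0.05, more than 80% power, 10-point difference, 15% attrition. The control rate is not stated; 35% is back-solved. With p1 = 0.35, p2 = 0.45 and mean 0.40:

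n per arm = [1.96·√(2·0.40·0.60) + 0.8416·√(0.35·0.65 + 0.45·0.55)]² / 0.10² = (1.358 + 0.580)² / 0.01 ≈ 376

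376 / 0.85 = 442.4, so 443 per arm and 886 in total. The figure reproduces. With 376 analysed per arm, power for a 10-point difference is 78–89% over control rates of 20–45%.

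**2. Responder test against a continuous test for the same effect.** Assume the HbA1c change is normal and convert the 10-point difference to a standardised shift d = z(p + 0.10) − z(p). Power ≈ Φ(d·√(376/2) − 1.96).

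| Control rate | d | Responder test | Change score |
|---|---|---|---|
| 20% | 0.317 | 88.8% | 99.2% |
| 30% | 0.271 | 82.1% | 96.1% |
| 40% | 0.253 | 78.8% | 93.5% |
| 45% | 0.251 | 78.4% | 93.1% |

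**3. Simulation of equation (1) and the alternatives.** All HbA1c inputs are assumptions. Baseline = 7.1 + Gamma(1.6, 1), so mean 8.7 and SD √1.6 = 1.26. Follow-up = m + slope × (baseline − 8.7) + N(0, residual SD) − effect in the treated, plus small clinic and quarter effects. Unless stated otherwise, slope is 0.5–0.7 and residual SD 1.0–1.2, which gives a baseline–follow-up correlation of 0.46–0.66. Values are rounded to 0.1 and response is a fall of 0.5 or more. There are 376 per arm, 20 clinics, and 1,200–1,500 trials per setting. Clinic is fitted as a fixed effect, which approximates the planned random effect. Entries are rejection rates.

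| Setting | Equation (1) | Plus baseline HbA1c | Continuous, baseline-adjusted |
|---|---|---|---|
| Effect 0.2%, control response 44–45% | 39–54% | 43–57% | 63–78% |
| Effect 0.2%, control response 34–37% | 35–52% | 38–54% | 61–78% |
| Effect 0.2%, slope 0.3 (old reading, more regression) | 33–41% | 40–52% | 63–76% |
| Effect 0.2%, slope 0.9–1.0, residual SD 1.0 | 58–60% | 59% | 77–79% |
| Effect 0.3%, control response 44–45% | 68–88% | 74–89% | 92–98% |
| Simulated difference 9–10 points, control about 35% | 75–77% | 78–83% | – |
| No effect | 4.0–5.9% | 4.3–6.0% | – |

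Within a setting, baseline adds 1–8 points at slope 0.5–0.7, 7–11 at slope 0.3, and about 0 at slope 0.9–1.0. At a true effect of 0.5% the responder test has at least 98% power. A repeat simulation agreed within Monte Carlo error: 34–56%, 40–58% and 60–79% at 0.2%, and 78–80% rising to 81–84% near the planned difference.

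**4. Closed-form check of the continuous column, effect 0.2%.** SE = residual SD × √(2/376). For SD 1.0, SE = 0.0729 and power = Φ(0.2/0.0729 − 1.96) = Φ(0.78) = 78%. For SD 1.2, SE = 0.0875 and power = Φ(0.33) = 63%.

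**5. How prognostic baseline is.** In a separate simulation (baseline normal, truncated above 7; correlation 0.3–0.7), control response was 18–32 points higher in the upper half of baseline HbA1c than in the lower half. Adding baseline to the logistic model gained about 2–7 points of power.

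**6. Chance imbalance.** The SD of the arm difference in mean baseline HbA1c is 1.26 × √(2/376) ≈ 0.09. A 2-SD imbalance moves the unadjusted response difference by about 1.5–3.3 percentage points, against a planned 10.

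**7. Cut-off.** With one-decimal reporting, 2.9–3.7% of simulated patients fall by exactly 0.5. Of 752 analysed, that is about 22 to 28 patients.

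**The case against.** The strongest reply is that the large contrast in power comes from changing the scale of the endpoint, not from the missing covariate. The trial was sized for a 10-point response difference, and a true 0.2% shift gives only about 6–7 points, so low power there follows mainly from the chosen target and endpoint. Larger effects are cited for patients with high values, and at 0.5% the planned test is ample. This stands: the defect in equation (1) itself costs only the 1–8 points.

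It is also right that the planned test keeps its error rate. Chance imbalance is already counted in its standard error, so step 6 shows the same loss in another form and is not a second harm.

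The assumed inputs do not cover every case. With slope 0.7 and residual SD 0.8, the three powers are about 70%, 74% and 93%. At slope 0.9–1.0 with residual SD 1.2, equation (1) has about 44%, so that row of the table holds only for SD 1.0. The direction of the continuous advantage does not change.

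The benefit of adding age, gender and BMI cannot be computed from the documents and is probably small. The clinic effect already reflects stratification by practice. The cut-off conflict is a small one, since the definition of Y and the power section agree.

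None of this supplies the missing covariate or the missing continuous analysis.

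**Conclusion.** The concern holds, as an improvement that should be made and not as a fault that invalidates the trial. Equation (1) omits baseline HbA1c and the matching factors, no continuous HbA1c analysis is prespecified, and the cut-off is stated in two ways. These points are certain from the text.

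The size of the benefit is less certain because every HbA1c input is assumed. Baseline adjustment of the responder model is worth about 1–8 points of power under the main assumptions, and from about 0 to 11 points over the wider range of slopes. A baseline-adjusted continuous analysis would raise power at a true 0.2% effect from 35–54% to 61–78%. The sample size is reproduced and the responder endpoint has a stated clinical rationale, so neither needs to change.

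**What to change.** - Keep the responder endpoint as primary and add baseline HbA1c, age, gender and BMI to equation (1).
- State which HbA1c reading is the baseline, since eligibility accepts one up to 12 months old. Use that same reading to compute Y and as the covariate.
- Report adjusted response rates or a risk difference beside the adjusted odds ratio.
- Prespecify, as a key secondary analysis, a linear mixed model of six-month HbA1c on treatment with the same covariates, practice and quarter. Making it primary is optional and would mean rewriting the hypothesis and power section.
- Use 0.5% or more in the hypothesis, as the model and power section already do.

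The cost is wording and one added analysis, with no new data and no change in sample size. The one drawback is that the adjusted odds ratio is conditional on the covariates and differs from the unadjusted one. In simulation at a 0.2% effect and a control response of about 35%, it was 1.33–1.42 against 1.28–1.36, which is why adjusted rates should be reported too.
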